**Proposal Summary** 

\*What type of study is your request? Clinical Study

\*Therapeutic Area Surgical

Surgical Area Retina

\*Proposal Title Comparison of beveled-tip vs. standard-tip

[figure not shown]
vitrectomy probe

\*Preferred submission option

High-speed beveled tip versus standard tip vitrectomy probe: a prospective randomized clinical trial

# **Background**

The Advanced Ultravit High-Speed Beveled Probe (Alcon) has a beveled-tip design that allows the cutting port to come closer to the retina compared to the previous vitrector probe design. This allows the surgeon to maneuver in tight tissue planes and increases the functionality of the vitrector probe. This in combination with the increased cut rate of 10,000 independent cuts per minute reduces traction on the retina and increases efficiency of vitreous removal.

### **Purpose**

-Compare the efficiency and safety of the new Utravit High-Speed Beveled Probe compared to the current standard vitrector probe.

# **Primary objectives:**

- -Time to completion of core vitrectomy
- -Time to completion of shave of vitreous base

## **Secondary objectives:**

- -Intraoperative complications (e.g. iatrogenic retinal breaks, intraocular bleeding, retinal detachment)
- -Postoperative complications

#### **Enrollment Period:**

9 months

## **Study Duration:**

12 months

### **Sample Size Calculation**

Target: 40 participants (20 in each cohort)

Assuming an average core vitrectomy time of 12 +/- 3 minutes, a sample size of at least 32 is needed to adequately assess for a clinically significant difference between the two groups with 80% power at a 95% confidence interval. A p-value of less than 0.05 will be deemed as statistically significant.

### **Study Design:**

This is a prospective, randomized controlled trial comparing the efficiency and safety of the Ultravit High-Speed Beveled Probe with the current Alcon vitrector probe in a cohort of patients undergoing routine vitrectomy surgery.

#### **Inclusion criteria:**

The study population will be male and female patients 18 years old or older with the presence of pathology requiring vitreoretinal surgery (vitreous opacities, vitreous hemorrhage, vitreomacular traction, macular hole, epiretinal membrane) without previous history of vitreoretinal surgery.

Written informed consent must be obtained before any enrollment in the study

#### **Exclusion criteria:**

- -Previous incisional intraocular surgery other than uncomplicated cataract surgery with intraocular lens placement
- -Inability to consent for procedure

# **Procedures and Assessments:**

All patients will undergo baseline testing in the study eye including:

- -BCVA
- -intraocular pressure
- -slit-lamp examination
- -360 degree indirect ophthalmoscopy

#### **Methods:**

On the day of surgery, patients will be randomized to the Ultravit High-Speed Beveled Probe or the current non-beveled Alcon Probe. All patients will undergo routine vitrectomy surgery as scheduled; patients will be masked to the vitrector probe used. Time to completion of vitrectomy and time to completion of vitreous base shave will be recorded by a masked timer.

All examination will be repeated as regularly scheduled postoperative visits by a masked reader. Safety will be assessed at each visit by evaluation for any adverse events.

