Identifiers: NCT04076072 Unique Protocol ID: 190728

Brief Title: High-speed Beveled Tip Versus Standard Tip Vitrectomy Probe: a Prospective Randomized Clinical Trial

Document Date: April 8, 2022

Statistical Analysis Plan

Objectives/Endpoints

IIT# 46218371 [[name]] High-speed beveled tip versus standard tip vitrectomy probe: a prospective randomized

Primary Objective:

 Intraoperative efficiency of vitrectomy surgery regarding time to completion of core vitrectomy and shave of vitreous base

Tissue-staining dyes will be used to visualize vitreous intraoperatively. These dyes aid in confirming completion of core vitrectomy and completion of vitreous shave. These factors will rely upon the judgement of the surgeon.

Exploratory Objective:

Intraoperative complications (e.g. iatrogenic retinal breaks, intraocular bleeding, retinal detachment)
 Postoperative complications

The study will not be sufficiently powered to assess safety. Surgeons will want to make sure there is no significant increase in complications with a different probe. However, any post operative complications would merely be an association, without any causality attributed.

Primary Endpoint:

A clinically significant difference between the two groups with 80% power at a 95% confidence interval.

A p-value of less than 0.05 will be deemed as statistically significant.

Alcon

1 | Subject | Date | Confidential - Business Use Only

Patient Selection Criteria

IIT# 46218371 [[name]] High-speed beveled tip versus standard tip vitrectomy probe: a prospective randomized

Inclusion Criteria	Exclusion Criteria
1. Adult (>18 years) 2. Presence of pathology requiring vitreoretinal surgery • Vitreous opacities • Vitreous hemorrhage • Vitreomacular traction • Macular hole • Epiretinal membrane 3. Subjects without previous history of retinal surgery 4. Ability to consent to procedure	Subjects with previous incisional intraocular surgery other than uncomplicated cataract surgery with IOL placement Inability to consent for procedure

5 | Subject | Date | Confidential - Business Use Only

Sample Size

IIT# 46218371 [[name]] High-speed beveled tip versus standard tip vitrectomy probe: a prospective randomized

Sample Size:

Target: 40 participants (20 in each cohort)

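### Does the missing start point for the two primary times leave it open whether shave time includes core time?

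*Protocol*

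**What the plan says.** The protocol's Primary objectives list two items: "Time to completion of core vitrectomy" and "Time to completion of shave of vitreous base". Each is named by its end only.

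The protocol's Methods section is the only place that describes recording: "Time to completion of vitrectomy and time to completion of vitreous base shave will be recorded by a masked timer". It gives no start, and it drops the word core from the first time.

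The SAP's Primary Objective puts both steps in one phrase: "Intraoperative efficiency of vitrectomy surgery regarding time to completion of core vitrectomy and shave of vitreous base". It then explains how the ends are recognised: "These dyes aid in confirming completion of core vitrectomy and completion of vitreous shave", with the surgeon making the judgement. The SAP's Primary Endpoint entry names no time at all. It reads "A clinically significant difference between the two groups with 80% power at a 95% confidence interval".

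The sample size, given in the same terms in both documents, rests on core time alone: "Assuming an average core vitrectomy time of 12 +/- 3 minutes", at least 32 patients, with a target of 40 (20 per arm).

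**The concern.** Time to completion of a later step has two natural meanings: the duration of that step, or the time elapsed since surgery began. The text allows both. On the second meaning, shave time contains core time and the two primary results are not separate evidence. A probe that speeds only the core would also appear to speed the shave.

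The SAP's phrase "time to completion of core vitrectomy and shave of vitreous base" can also be read as one combined time. The sample size would not cover such a time, because its only spread is that of the core. The Primary Endpoint entry is where a reader would expect this to be settled, and it is silent.

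These are the trial's only primary measures, so an unclear definition deserves a check.

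**Working it through.** **1. The plan's own figure.** Inputs from Sample Size Calculation: SD 3 minutes (the figure after +/- is taken as an SD), 80% power, alpha 0.05 (taken as two-sided), at least 32 patients, so 16 per arm. No difference in minutes is given, so it has to be back-solved:

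- Normal approximation: 3 × (1.960 + 0.842) × √(2/16) = 2.97 minutes.
- t-test: 3.07 minutes.
- Forward check with a 3-minute difference: 2 × (1.960 + 0.842)² × 3²/3² = 15.7, rounded up to 16 per arm, or 32 in all.

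A 3-minute core difference is therefore a fair working value. It is inferred, not stated.

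**2. What a cumulative clock would do.** Assume a 3-minute core saving, no shave saving, core SD 3 and 20 per arm. The documents give neither the shave SD (s) nor the core–shave correlation (ρ), so both are assumed. The SD of cumulative time is √(9 + s² + 2ρ·3·s). At s = 3 and ρ = 0 it is √18 = 4.24 minutes. Chance of p<0.05 (two-sided t-test):

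| Time analysed | Chance of p<0.05 |
|---|---|
| Core | 87% |
| Shave on its own clock | 5% |
| Cumulative, s = 3, ρ = 0 | 59% |
| Cumulative, s = 1.5, ρ = 0 (highest) | 79% |
| Cumulative, s = 6, ρ = 0.3 (lowest) | 24% |

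In this scenario the cumulative times really do differ by 3 minutes, so the test is right to reject. The only error would be to call that difference a shave saving.

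**3. Can the shave interval be recovered?** Let C be the reading at completion of the core and V the reading at completion of the shave.

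- Separate clocks: V is already the shave interval, and C + V is the total.
- One running clock: V is the total, and V − C is the shave interval.

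Methods has both readings taken, so either convention yields the other. The condition is that the shave follows the core directly. Any step between them would fall into V − C.

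**4. One time or two?** The protocol's objectives give two separate items. Methods repeats the words for time to completion before each item and has both recorded. Right after its objective, the SAP names the completion of each step separately and then refers to them in the plural. Against this stands one compressed phrase in the SAP. The two-time reading is clearly the intended one.

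**5. The sample-size argument.** The calculation uses only the spread of core time. It therefore covers a stand-alone shave time no better than a combined one. The gap is the same under every reading and does not measure harm from the unclear start.

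**The case for a change.** The strongest case for a change is that two readings of a primary measure are both open and that closing the gap is cheap: a sentence on start and stop points, one extra time stamp taken by the timer already planned, and no added patients or staff. A written start would help recording to be consistent and would tell readers what a shave saving means. The fact that two times are listed does not settle whether the second includes the first.

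Most of this stands as description. The available text does not say when either clock starts, and the Primary Endpoint entry does not name a variable. A stated definition would be tidier.

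The consequence does not stand. Harm requires an analyst to hold both readings, report a cumulative one as the duration of the shave, and not subtract. Nothing in the documents points that way. Nor do the documents favour one convention: a shave clock with its own start, and a running clock with the difference reported, are both sound.

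One limit applies to the absence itself. The SAP text comes from slides whose footers go from 1 to 5, so the claim can only be that no start appears in the text available.

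**Conclusion.** The observation is correct, but no change follows. This is a gap in detail that the study team can be expected to fill sensibly. The ends of both steps are described, both times are recorded, and the shave interval can be had directly or by subtraction. No stated rule gives a wrong answer. The missing word in Methods is clerical, since the objectives and the sample size both refer to core vitrectomy. The combined-time reading is weak, and its sample-size argument applies equally to a stand-alone shave time.

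The size of any effect cannot be stated from the documents, which give no mean, SD or expected saving for the shave. The 24% to 79% range rests on an assumed shave SD of 1.5 to 6 minutes, a correlation of 0 to 0.3, no shave effect and a 3-minute core effect inferred from the sample size. It shows how far a mislabelled time could mislead, not an error rate of the plan. The conclusion assumes that the shave follows the core without a substantial step between them, or else that the shave was timed from its own start.

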Identifiers: NCT04076072 Unique Protocol ID: 190728

Brief Title: High-speed Beveled Tip Versus Standard Tip Vitrectomy Probe: a Prospective Randomized Clinical Trial

Document Date: April 8, 2022

Statistical Analysis Plan

Objectives/Endpoints

IIT# 46218371 [[name]] High-speed beveled tip versus standard tip vitrectomy probe: a prospective randomized

Primary Objective:

 Intraoperative efficiency of vitrectomy surgery regarding time to completion of core vitrectomy and shave of vitreous base

Tissue-staining dyes will be used to visualize vitreous intraoperatively. These dyes aid in confirming completion of core vitrectomy and completion of vitreous shave. These factors will rely upon the judgement of the surgeon.

Exploratory Objective:

Intraoperative complications (e.g. iatrogenic retinal breaks, intraocular bleeding, retinal detachment)
 Postoperative complications

The study will not be sufficiently powered to assess safety. Surgeons will want to make sure there is no significant increase in complications with a different probe. However, any post operative complications would merely be an association, without any causality attributed.

Primary Endpoint:

A clinically significant difference between the two groups with 80% power at a 95% confidence interval.

A p-value of less than 0.05 will be deemed as statistically significant.

Alcon

1 | Subject | Date | Confidential - Business Use Only

Patient Selection Criteria

IIT# 46218371 [[name]] High-speed beveled tip versus standard tip vitrectomy probe: a prospective randomized

Inclusion Criteria	Exclusion Criteria
1. Adult (>18 years) 2. Presence of pathology requiring vitreoretinal surgery • Vitreous opacities • Vitreous hemorrhage • Vitreomacular traction • Macular hole • Epiretinal membrane 3. Subjects without previous history of retinal surgery 4. Ability to consent to procedure	Subjects with previous incisional intraocular surgery other than uncomplicated cataract surgery with IOL placement Inability to consent for procedure

5 | Subject | Date | Confidential - Business Use Only

Sample Size

IIT# 46218371 [[name]] High-speed beveled tip versus standard tip vitrectomy probe: a prospective randomized

Sample Size:

Target: 40 participants (20 in each cohort)

Assuming an average core vitrectomy time of 12 +/- 3 minutes, a sample size of at least 32 is needed to adequately assess for a clinically significant difference between the two groups with 80% power at a 95% confidence interval. A p-value of less than 0.05 will be deemed as statistically significant.

Alcon

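### Two primary times share one unadjusted p<0.05 with no order, alpha split or either/both rule in the posted text, and neither clock has a stated start

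*SAP*

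**What the plan says.** The protocol's Primary objectives section has two bullets of equal standing: "Time to completion of core vitrectomy" and "Time to completion of shave of vitreous base". The SAP joins them in one primary objective, "Intraoperative efficiency of vitrectomy surgery regarding time to completion of core vitrectomy and shave of vitreous base".

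The SAP's Primary Endpoint reads "A clinically significant difference between the two groups with 80% power at a 95% confidence interval". This names no variable and no test. The significance criterion is "A p-value of less than 0.05 will be deemed as statistically significant", and the sample size sections of both documents repeat it.

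The sample size rests on core time only: "Assuming an average core vitrectomy time of 12 +/- 3 minutes, a sample size of at least 32 is needed". The target is 40 patients, 20 per arm. No mean, SD or difference is given for shave time.

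On measurement, the protocol's Methods section says "Time to completion of vitrectomy and time to completion of vitreous base shave will be recorded by a masked timer". The SAP adds "These dyes aid in confirming completion of core vitrectomy and completion of vitreous shave" and leaves both completion points to the surgeon's judgement. Neither document says when either clock starts.

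**The concern.** With two primary outcomes and one threshold, the plan has to say what counts as success, and the posted text does not. The choice between either time, both times and core time first can therefore be made after the results are known. If a significant result on either time is accepted, the chance of a false claim exceeds the nominal 5%.

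The undefined clocks add a problem of interpretation. If shave time runs from the start of surgery, it contains core time and any effect on it. If it runs from the end of the core step, it depends on when the surgeon calls that step finished. The two versions answer different questions, and the plan does not say which one is primary.

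**Working it through.** **Inputs from the documents:** 12 +/- 3 minutes for core time, minimum 32 patients, target 20 per arm, 80% power, 95% confidence, p<0.05.

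**Assumptions, because the documents are silent:** 3 minutes is the SD; the difference sought is 3 minutes (1 SD); tests are two-sided; the correlation between the two times is between 0 and 0.95.

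**1. The plan's own figure.** n per arm = 2 × (1.960 + 0.842)² × 3² / 3² = 15.7, rounded up to 16, or 32 in total. This matches the stated minimum, but only because a 3-minute difference was assumed. The t-test version gives 17 per arm (34 in total). At the target of 20 per arm, t-test power for core time is 86.9%.

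**2. Either time suffices, no true effect.** For independent tests the error is 1 − 0.95² = 9.75%. For correlation ρ it is 1 − P(|Z₁| < 1.96 and |Z₂| < 1.96), with Z₁ and Z₂ bivariate normal:

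| ρ | Family-wise error |
|---|---|
| 0 | 9.75% |
| 0.5 | 9.07% |
| 0.7 | 8.35% |
| 0.9 | 7.04% |
| 0.95 | 6.46% |

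Simulated pooled t-tests at 20 per arm agree: 9.75%, 9.1%, 8.4% and 7.1% at ρ = 0, 0.5, 0.7 and 0.9. Counting only false claims in favour of the beveled probe, the simulated rates are 4.9%, 4.5%, 4.2% and 3.5%, against 2.5% for a single two-sided test.

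**3. Both times required.** Error cannot exceed 5%. Power for the joint claim cannot be derived from the documents, because shave time has no sizing inputs. As an illustration, with a 1-SD effect on each of two separately clocked times, simulated joint power at 20 per arm is 76% at ρ = 0 and 83% at ρ = 0.9. It reaches 80% at a correlation of about 0.7, so on these assumptions the shortfall is small.

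**4. Core power under each remedy, 20 per arm, 1-SD core effect.**
- Core first, then shave: 86.9%, unchanged.
- Holm, shave also has a 1-SD effect: 82.8% to 85.3%, a loss of 1.6 to 4.1 points.
- Holm, no shave effect: about 79.3%, a loss of 86.9 − 79.3 = 7.6 points.

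**5. The clocks.** Assume equal SDs for the two steps, a 1-SD core effect and no shave effect. A cumulative shave time then differs between arms by 1/√2 = 0.71 SD if the steps are independent, or 1/√3 = 0.58 SD if they correlate at 0.5. Core and cumulative shave times are then both significant in 57% or 43% of simulated trials, against about 4% when the shave step is timed alone.

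In the other direction, assume an SD of 3 minutes per step, independent steps, no true effect, and core declared finished 1 minute earlier in the beveled arm. Core time then favours the beveled probe in about 17% of trials instead of 2.5%. The time from the start of surgery to the end of the shave stays at 2.5%.

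**The case against.** **Core time is already the lead, because the sample size uses it.** This is a reasonable guess at intent. But no sentence says so, and both objective statements give the two times equal rank.

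**The SAP may mean one combined time, or may require both.** Either reading removes the inflation, and the SAP's wording allows them. However, no combined time is defined, and the protocol lists and records the two times separately. This objection makes the 7% to 10% conditional; it does not supply the missing rule.

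**The Primary Endpoint also asks for clinical significance.** If that meant an observed margin, error could be far lower. With an assumed margin of 3 minutes, 3 / (3 × √(2/20)) = 3.16 standard errors, a two-sided probability of about 0.0016 per time, or about 0.3% for two. But no margin is stated, so it cannot serve as a decision rule.

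**A cumulative clock yields false shave claims.** A reader might infer this from the 57% and 43% above. The documents do not support it. If the time runs from the start of surgery, a faster core step really does shorten it, so those figures are power for a true difference in total time. What can mislead is calling that result a shave effect.

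**Step-wise timing should therefore be required.** A reader might infer this too. It does not follow: completion rests on the surgeon's judgement, and Methods describes masking of the patient, the timer and the reader but does not mention the surgeon. Moving the boundary moves minutes from one step-wise time to the other.

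**Conclusion.** The concern holds for the posted text. Two primary times are named, one unadjusted threshold is given, and the rule connecting them is missing. The size is conditional: family-wise error is about 7% to 10% if either time suffices and the correlation is between 0 and 0.9, falling towards 5% above that. If both are required, error is controlled, and the gap is that the 80% power describes core time only.

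A reader might infer that the trial's error rate is definitely inflated, or that the full plan has no multiplicity rule. Neither can be concluded. The either-suffices reading is one of several that the text allows, and the jump in SAP slide footers from 1 to 5 means that slides may be missing from view.

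The clock gap is one of definition and applies to both times. Methods also refers to vitrectomy where the objectives refer to core vitrectomy. The gap is not in itself an error-rate problem. The point should be fixed; the trial remains usable.

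**What to change.** In the SAP, state that:
- core time is tested first at two-sided 0.05, as the only time with sizing inputs;
- shave time is tested at two-sided 0.05 only if core time is significant, and is otherwise reported as an estimate with a 95% CI;
- the 80% power refers to core time only.

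In the protocol's Methods and in the SAP, give the start point of both clocks and say whether shave time is cumulative or step-wise. Either is acceptable if stated. A cumulative time must be labelled as total time, because it includes any core effect. A step-wise time should carry the caveat that it depends on the surgeon's call of the boundary between core and shave. Report the other version as supportive, by subtraction or addition where the steps are consecutive.

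If outcome data had been seen when the rule is added, label it as set afterwards.

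**Cost:** a few sentences, no extra patients and no loss of core power. The downside of the fixed order is that there is no confirmatory shave claim if core time is not significant. With an assumed 0.5-SD core effect and 1-SD shave effect on separate clocks, a shave claim follows in 29% to 34% of trials, against 79% to 81% with Holm. If a shave-only claim matters to the sponsor, Holm across both times is the alternative, at about 2 to 8 points of core power.

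### Does the SAP wrongly disclaim causality for complications in a randomised comparison of the two probes?

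*SAP*

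**What the plan says.** The SAP places intraoperative and postoperative complications under its exploratory objective and follows the list with three sentences. The first concedes the limit: "The study will not be sufficiently powered to assess safety". The second says why the data are of interest: "Surgeons will want to make sure there is no significant increase in complications with a different probe". The third is the one in question: "However, any post operative complications would merely be an association, without any causality attributed".

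The Protocol gives safety more prominence. Its Purpose is to "Compare the efficiency and safety of the new Utravit High-Speed Beveled Probe compared to the current standard vitrector probe", and it lists complications as secondary objectives. Under Methods, "On the day of surgery, patients will be randomized to the Ultravit High-Speed Beveled Probe or the current non-beveled Alcon Probe". On masking, "patients will be masked to the vitrector probe used", and "All examination will be repeated as regularly scheduled postoperative visits by a masked reader". The next sentence reads "Safety will be assessed at each visit by evaluation for any adverse events", without saying whether that evaluator is masked. Masking of the surgeon is not stated.

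Neither document names a summary measure, interval or test for complications.

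**The concern.** The disclaimer comes straight after a sentence about an increase with a different probe and is joined to it by *However*. Taken that way, its subject is the comparison of the two arms, and a warning of mere association belongs to a non-randomised study. Allocation here is random, so a difference in complication risk estimates an effect of probe assignment. What weakens it is the small sample, an open list of complication types and masking that is only partly described.

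Two misreadings would be possible. A non-significant difference might be taken as reassurance, because the preceding sentence speaks of no significant increase. A marked difference might be set aside as non-causal. Since safety is half of the Protocol's stated purpose, that deserves a check.

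**Working it through.** **The two readings.** The disputed sentence carries no figure, so the main check is textual.

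- *Between-probe reading.* It is supported by the preceding sentence and by *However*. On this reading the caveat does not fit a randomised design.
- *Single-event reading.* The grammatical subject is complications, meaning events, not a rate or a difference. *Attributed* is the usual word for assigning a cause to an event. The sentence covers postoperative complications only, although intraoperative ones are listed just above. If it were about the randomised comparison there would be no reason to leave those out. On this reading the statement is sound, since one patient's postoperative complication cannot be ascribed to the probe by the design.

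The text does not settle which is meant. It is ambiguous, not shown to be wrong.

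**Is the right caveat already present?** The inputs are 20 per arm (SAP, Sample Size) and a significance level of 0.05, taken as two-sided. The documents give no complication rates, so the rates and counts below are assumptions.

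The Newcombe interval uses the Wilson limits (l, u) of each arm, with d = p1 - p2:

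- lower = d - √[(p1 - l1)² + (u2 - p2)²]
- upper = d + √[(u1 - p1)² + (p2 - l2)²]

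*0/20 v 0/20.* The Wilson upper limit is z²/(n + z²) = 3.8415/23.8415 = 0.161 in each arm, so the interval is -16.1 to +16.1 points.

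*4/20 v 1/20.* The Wilson limits are 0.081 to 0.416 and 0.009 to 0.236, and d = 0.15.

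- lower = 0.15 - √(0.119² + 0.186²) = -0.071
- upper = 0.15 + √(0.216² + 0.041²) = +0.370

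Fisher's exact p is 0.34.

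Power of two-sided Fisher's test at 20 per arm, by enumerating all 21 × 21 outcomes:

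| Assumed rates | Power | Chance that p ≥ 0.05 |
|---|---|---|
| 5% v 15% | 7% | 93% |
| 10% v 30% | 24% | 76% |
| 20% v 60% | 65% | 35% |

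For 80% power by the normal approximation, n per arm = [1.96√(2p̄q̄) + 0.8416√(p1q1 + p2q2)]²/(p1 - p2)²:

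- 5% v 15%: (0.8316 + 0.3521)²/0.01 = 140.1, so 141
- 10% v 30%: (1.1088 + 0.4610)²/0.04 = 61.6, so 62

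All of this confirms that 20 per arm is too few for safety, as the SAP itself states. None of it measures the effect of the causality sentence, which has no numerical size.

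**Could the sentence alter a planned result?** It could do so only by modifying a rule. The SAP sets no safety test, margin or pass criterion, and the remark about what surgeons will want explains why complications are recorded.

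**The case for a change.** The strongest reply concerns a clear difference. With 5/20 v 0/20 the risk difference is +25 points (Newcombe +3.8 to +46.9; Fisher p = 0.047). On the between-probe reading, the SAP would have that treated as mere association although patients were randomised. It can also be said that a sentence needing interpretation should be clarified whichever reading is right, and that naming a risk difference with an interval costs nothing.

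Part of this stands. The wording is loose on the between-probe reading, and the missing summary measure is a real omission. But a difference of that kind would be visible in the arm counts whatever the SAP says about causality, and readers will know the trial was randomised. Some reserve about an isolated finding is also fair. With equal true rates of 10% and independent complication types, the two-sided error per type is 0.0118 for Fisher's test and 0.0387 for uncorrected chi-square. The chance of at least one p < 0.05 among six types is then 1 - (1 - 0.0118)⁶ = 6.9% or 1 - (1 - 0.0387)⁶ = 21%. Six is illustrative, since the documents fix no number of types. Unstated masking of the surgeon is a further reason for care with surgeon-judged events, though it does not undo randomisation.

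**Conclusion.** No change to the plan is called for. The sentence is wrong only on one of two tenable readings, and even then it errs towards claiming too little about an outcome the SAP ranks as exploratory. The caveat that matters, imprecision, is already in the same paragraph as a statement of insufficient power.

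The unstated summary measure is a gap that analysts fill sensibly: counts by randomised arm and, if a difference is quoted, an interval that copes with sparse events. A Wald interval would not, since it has zero width at 0/20 v 0/20. A non-significant difference should not be read as equal safety, and nothing in the SAP says that it may be. The different ranking of complications, secondary in the Protocol and exploratory in the SAP, is a separate matter of tidiness.

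The effect on the target of 40 participants, the primary endpoint and any stated result is nil. This conclusion rests on the absence of a safety decision rule. The illustrative intervals and powers rest on assumed counts and rates.
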